6.7 ADJUVANT THERAPIES

6.7.1 RADIATION:

Following standard pathologic assessment, patients will be assessed for any adverse features that would warrant adjuvant whole breast radiation with or without regional

nodal radiation. This would include margins <2mm, positive lymph nodes, or as recommended by treating radiation oncologist due to any other adverse feature identified. Hypofractionated and conventionally fractionated regimens (40.50-50 Gy) can be considered by the treating radiation oncologist. In these patients requiring adjuvant radiation, a boost will not be delivered.

6.7.2 ADJUVANT SYSTEMIC THERAPY

Adjuvant systemic therapies including chemotherapy and endocrine therapy will be at the discretion of the medical oncologist. If Oncotype DX or other genetic scoring is desired for evaluation, this will be sent on the pre-treatment biopsy specimen obtained before enrollment on study and which was used for initial diagnosis. Medical oncology approval via case discussion or formal consultation is required prior to pre-operative SBRT to ensure the medical oncologist will be able to obtain all needed information to determine adjuvant systemic recommendations.

6.8 CRITERIA FOR DISCONTINUATION FROM PROTOCOL TREATMENT.

Because SBRT is delivered in one day, discontinuation is unlikely. However if at any time the constraints of this protocol are detrimental to the patient's health and/or the patient no longer wishes to continue on the study long-term, the patient shall be removed from the protocol follow-up. In this event the reason(s) for discontinuation of study participation will be noted by the PI in the Radiation Oncology record. Subjects who prematurely withdraw will not be replaced unless radiation has not been initiated. Reasons for PI-initiated withdrawal may include, but is not limited to the following:

- Adverse events
- Abnormal laboratory values
- Abnormal test procedure results
- Protocol deviation
- Administrative issues
- Disease progression

6.9 DURATION OF THERAPY:

The duration of protocol-specified therapy will be approximately 2 months. It is expected that treatment planning may take 2 weeks from simulation to treatment delivery, and that 4-6 weeks will elapse from treatment delivery to surgery.

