2.2 SECONDARY OBJECTIVES

2.2.1 To determine the rate of severe acute toxicity, defined as any CTCAE v4 grade 3 or higher toxicity noted from RT delivery up to 90 days after completion of surgery.

2.2.2 To determine the rate of poor cosmetic outcomes from both provider and patient perspectives up to 3 years after pre-operative SBRT to intact breast tumors using the RTOG (Radiation therapy oncology group) cosmesis scale and digital images.

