13. STATISTICAL CONSIDERATIONS

This is a prospective, single-arm study to determine the pathologic outcomes, acute toxicities, cosmetic outcomes, and local recurrence rates of preoperative single fraction partial breast radiation in early stage breast cancer. All analyses will be undertaken in the enrolled population who initiate treatment.

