13.2 Analysis of secondary objectives

Acute toxicities (up to 90 days after completion of surgery) will be collected using CTCAE v4.0 and will be tabulated by body system, type and grade. The number and percentage of patients who experience at least one grade 3 or higher AE will also be reported. The presence or absence of all CTCAE toxicities included in Appendix 15.2 will be assessed in addition to those listed here: breast pain, dermatitis, atrophy, fatigue, fibrosis, lymphedema, pruritis, seroma, surgical wound dehiscence, fat necrosis, surgical site infection, hyperpigmentation, skin ulceration. We will use continuous toxicity monitoring throughout the trial as described below. Stopping rules are described below in 13.3.

Local recurrence rates will be calculated using cumulative incidence function, where death without local recurrence is considered as competing event. The associated 95% confidence intervals at landmark timepoints including 6 months, 1 year, 2 years and 3 years will also be provided.

Physician assessment of cosmesis (see Section 9.3) will occur at baseline, 4-6 weeks after surgery, 6 months, 1, 2 and 3 years. The secondary endpoint of poor cosmetic outcome is a physician-assessment of unacceptable (fair or poor) cosmesis at any time point through 3 years and/or occurrence of grade 3 or higher toxicity through 3 years. The number and percentage of patients, with 2-sided x% CIs, will be reported. The timepoint of unacceptable cosmesis assessment and of the grade 3 or higher AEs will be summarized descriptively. Additionally, when all enrolled subjects have had 1 year of follow-up, a working group of investigators will be assembled to evaluate cosmesis on all patients.

Patient-reported satisfaction with cosmetic outcome will be assessed at baseline, 6 months, 1, 2 and 3 years. Satisfaction over time will be summarized descriptively and graphically.

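### Section 6.8 does not separate stopping protocol treatment from ending outcome follow-up, so the 3-year cosmesis composite and some local recurrences can be under-counted

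*Combined protocol and SAP*

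**What the plan says.** Section 6.8 opens by noting "Because SBRT is delivered in one day, discontinuation is unlikely". It then names two triggers: the protocol's constraints harming the patient's health, and the patient no longer wishing to stay on study. In either case "the patient shall be removed from the protocol follow-up", and the investigator records why study participation ended. On replacement: "Subjects who prematurely withdraw will not be replaced unless radiation has not been initiated". The paragraph ends "Reasons for PI-initiated withdrawal may include, but is not limited to the following", followed by six reasons: adverse events, abnormal laboratory values, abnormal test results, protocol deviation, administrative issues and disease progression.

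The outcomes that depend on follow-up are these:

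- **Acute toxicity** (section 2.2.1): "defined as any CTCAE v4 grade 3 or higher toxicity noted from RT delivery up to 90 days after completion of surgery".
- **Poor cosmetic outcome** (section 13.2): a physician rating of fair or poor "at any time point through 3 years and/or occurrence of grade 3 or higher toxicity through 3 years".
- **Local recurrence** (sections 6.10 and 13.2): checked at each on-protocol visit and estimated by cumulative incidence to 3 years, "where death without local recurrence is considered as competing event".

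Section 13 sets the population: "All analyses will be undertaken in the enrolled population who initiate treatment". It has no rule for patients whose follow-up stops early. Section 10.1 collects adverse events through 90 days after surgery, follows ongoing related events beyond that, and asks participants to report serious related events after the study.

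**The concern.** A withdrawal rule normally separates two acts: stopping treatment and stopping observation. Section 6.8 runs them together. Once the single fraction and surgery are over, little protocol treatment is left to stop, so what a withdrawal removes is mainly the remaining calendar visits.

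Two of the listed reasons are related to the outcomes. A patient with a troublesome lower-grade adverse event may be more likely than others to be rated fair or poor later, or to develop a late grade 3+ event. A patient with nodal or distant progression may be more likely to recur in the breast. If such patients leave observation first, the later event is never recorded. The reported 3-year rates would then look better than the true ones, and lost patients are not replaced once radiation has begun.

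**Working it through.** **1. The primary endpoint.** The plan gives no figure for withdrawal; its only operating characteristics concern the primary test. The exact two-stage probability is the sum over x = 2 to 16 of P[Bin(16, p) = x] × P[Bin(24, p) ≥ 7 − x]. It gives 0.0890 at p = 0.10 and 0.8690 at p = 0.25, matching the stated 0.089 and 86.9%. RCB is read at surgery, so later withdrawal cannot change it. If 1, 2 or 4 second-stage patients left before surgery and were counted as non-responders, power would be 85.7%, 84.3% or 80.9%, an error against the treatment rather than for it.

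**2. Which secondary events can be lost.**

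| Reason for withdrawal | Already counted | Can be lost |
|---|---|---|
| Grade 3+ adverse event | Yes, in the acute rate (if within 90 days of surgery) and in the composite | Nothing further for the composite |
| Grade 1–2 adverse event | No | Later fair or poor rating; late grade 3+ event |
| Local recurrence | Yes, it is the event | Later cosmesis or late toxicity, if not already an event |
| Nodal or distant progression | No | Later local recurrence; later cosmesis or toxicity |

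**3. Cosmesis composite (assumed values).** The documents give neither a withdrawal rate nor an event rate. Assume 6 of 40 patients would truly meet the composite, 6/40 = 15%, and that w of those 6 are withdrawn for lower-grade events before any qualifying score or event. The reported rate is (6 − w)/40 if they are kept as non-events and (6 − w)/(40 − w) if they are dropped.

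| w | Kept as non-events | Dropped |
|---|---|---|
| 0 | 6/40 = 15.0% | 6/40 = 15.0% |
| 1 | 5/40 = 12.5% | 5/39 = 12.8% |
| 2 | 4/40 = 10.0% | 4/38 = 10.5% |
| 3 | 3/40 = 7.5% | 3/37 = 8.1% |

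Each lost event is 1/40 = 2.5 points when the denominator stays at 40. Two contrasts show what drives this. If both withdrawals at w = 2 were for grade 3+ events, those patients already meet the composite and the result stays 6/40 = 15%. If the two withdrawn patients were not heading for a poor outcome and were dropped, the result would be 6/38 = 15.8%, slightly too high. The favourable direction therefore depends on the withdrawn patients being at higher risk than the rest.

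**4. Local recurrence (assumed values).** Suppose a fraction f of would-be local recurrences is preceded by nodal or distant progression that leads to withdrawal, with no deaths. The observed hazard is then (1 − f) times the true one, and the 3-year estimate is 1 − (1 − true)^(1 − f).

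| True 3-year rate | f = 10% | f = 25% | f = 50% |
|---|---|---|---|
| 5% (2 of 40) | 4.5% | 3.8% | 2.5% |
| 10% (4 of 40) | 9.0% | 7.6% | 5.1% |

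This takes withdrawn patients to be censored, which is the usual handling under cumulative incidence but is not stated in the plan.

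**The case against.** The strongest reply is that section 6.8 does not say an adverse event or progression ends outcome collection. Removal from follow-up is tied to harm from the protocol's constraints or to the patient's own wish. The investigator's list comes later, is permissive, and stands under a heading about treatment. That is fair, and it means the loss is permitted rather than required. It does not close the gap: the sentence after removal speaks of ending participation in the study, and no other section says that cosmesis or recurrence data continue to be collected for such patients.

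Several stronger readings are tempting, and the documents do not support them:

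- A reader might infer that all three secondary rates are biased. The acute rate is little exposed, because a grade 3+ event that prompts withdrawal has already happened and section 10.1 collects adverse events to 90 days after surgery.
- A reader might infer that section 10.1 protects only ongoing related events. It also asks for serious related post-study events. These are safety-reporting provisions, however, and do not supply cosmesis scores or recurrence status.
- A reader might count protocol deviation as outcome-driven removal. It is not a measured outcome; it is discretionary removal that could be selective.
- A reader might fault the choice of death as the competing event. That choice is ordinary. What is missing is a rule for withdrawn patients.

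It also stands that these patients are described in section 3.3 as low risk, that reasons for discontinuation are already recorded, and that few patients may be affected.

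**Conclusion.** The point holds in limited form. Section 6.8 allows follow-up to end for reasons related to later outcomes, and section 13 does not say how such patients are analysed. The results at risk are the 3-year composite of poor cosmesis or grade 3+ toxicity, chiefly after lower-grade adverse events, and local recurrence after nodal or distant progression. Under-counting would favour the treatment if the withdrawn patients are at higher risk than those who remain.

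The bias is possible, not demonstrated, and its size cannot be derived from the documents. The fall from 15% to about 10% rests on three assumptions: six true events, two withdrawals for lower-grade events among those six, and withdrawal before a qualifying score. With so few patients, one or two such withdrawals would be visible in the reported rate. The amendment is worth making because it is cheap and the lost data could not be recovered afterwards.

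**What to change.** Amend section 6.8 so that investigator-initiated withdrawal for an adverse event, protocol deviation or progression applies to protocol treatment only. Toxicity, cosmesis and recurrence should continue to be collected to month 36 unless the patient withdraws consent for follow-up, is lost or dies. Record the date and reason in each case.

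In section 13.2, state how patients with incomplete follow-up enter the cosmesis denominator and the cumulative incidence estimate, including when they are censored. A simple bounding analysis would help: count incomplete patients first as non-events and then as events. In the illustration with two such patients this gives 4/40 = 10% and 6/40 = 15%, a range that contains the true value.

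The cost is a wording change in two sections and a small amount of extra data collection for the few patients concerned, at visits already in the study calendar. The change concerns data collection and analysis and alters no clinical management.

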6.10 DURATION OF FOLLOW-UP

October 10, 2023

Principal Investigator: [name]

IRB IRB00128074

Follow-up for this study includes physical exam by member of oncology team every 6 months for the first 2 years, every 6-12 months through year 5, and annually through year 10. Bilateral mammogram will be obtained annually. Other laboratory or radiographic studies will be obtained as directed by patient symptoms or physical exam. Quality of life and cosmetic assessments by both physician and patient will be performed at 6 months, 1 year, and then annually through 3 years of follow-up. Loco regional recurrence will be monitored on protocol at each follow-up visit. Please see study calendar, section 8.0, for detail. Standard follow-up should continue per NCCN guidelines, off protocol, after 3 years.

7. EXPECTED TOXICITIES

7.1 POSSIBLE TOXICITIES FROM RADIATION

7.1.1 Potential Short Term Reactions

Common:

- Skin redness and irritation in area treated
- Darkened skin and dryness in area treated
- Fatigue
- Temporary hair loss in the area treated
- Occasional aches and pains in the breast
- Temporary edema in treated breast

Uncommon:

- Post-operative bleeding at the time of surgery
- Increased risk of post-operative wound infection
- Seroma formation
- Skin blistering or ulceration

7.1.2 Potential Long Term Reactions

Common:

- Minor pigment change in the treated breast
- Occasional discomfort and sensitivity in the treated area
- Mild to moderate increased firmness of the treated breast
- Mild swelling of the treated breast which can last a number of years
- Minor shrinkage of the treated breast

Uncommon:

- Significant increase in firmness or fibrosis of the treated breast

October 10, 2023

Principal Investigator: [name]

IRB IRB00128074

- Significant shrinkage of the treated breast
- Breast Pain

Rare:

- Lung inflammation and scarring
- Rib fractures in the treated area

Extremely Rare:

- Damage to the heart causing heart failure or heart attack
- Tumors caused by radiation
- Damage to the nerves of the arm

8. STUDY CALENDAR

In order to minimize the need for research-only in-person visits, telemedicine visits may be substituted for in person clinical trial visits or portions of clinical trial visits where determined to be appropriate and where determined by the investigator not to increase the participants risks. Prior to initiating telemedicine for study visits the study team will explain to the participant, what a telemedicine visit entails and confirm that the study participant is in agreement and able to proceed with this method. Telemedicine acknowledgement will be obtained in accordance with the Guidance for Use of Telemedicine in Research. In the event telemedicine is not deemed feasible, the study visit will proceed as an in-person visit. Telemedicine visits will be conducted using HIPAA compliant method approved by the Health System and within licensing restrictions.

October 10, 2023

Principal Investigator: [name]

IRB IRB00128074

	Pre-SBRT (baseline)	SBRT	Post-SBRT ≤ 1 week prior to surgery	Surgical Procedure	4-6 weeks Post- Surgery	From time of surgery. All visits have a window of +/- 1 Month except where indicated					
						Month 6	Month 12	Month 18	Month 24	Month 30	Month 36
History/Physical	X ^a				X	X	X	X	X	X	X
Vitals signs, height weight	X				X	X	X	X	X	X	X
Demographics	X										
Breast imaging (mammogram minimum)	X ^a						X (+/- 3 months)		X (+/- 3 months)		X (+/- 3 months)
Core Biopsy/fiducial markers	X ^b										
Medical Oncology Approval	X										
Planning MRI	X										
Patient Questionnaire (BCTOS)	X ^d				X	X	X		X		X
Patient Cosmesis evaluation (RTOG)	X ^e				X	X	X		X		X
Physician Cosmesis evaluation (RTOG)	X ^e				X	X	X		X		X
Digital image of breasts	X						X				X
Performance Status (KPS)	X				X	X	X	X	X	X	X
Toxicity Assessment	X ^c		X ^c		X	X	X	X	X	X	X

a. Physical exam by member of oncology team every 6 months for the first 3 years.

Bilateral mammogram annually for the first 3 years. Follow-up will continue per NCCN guidelines, off protocol, after 3 years.

b. Verify placement of a biopsy clip at diagnostic procedure and availability of pre-treatment tissue for correlative science.

October 10, 2023

Principal Investigator: [name]

IRB IRB00128074

- c. Post-SBRT toxicity evaluation in Radiation Oncology within 1 week prior to surgery and again 4-6 weeks after surgery.
- d. BCTOS to be completed by patient at baseline (prior to treatment), at first FU 4-6 weeks after surgery, six months and one year after surgery, and then annually for 2 additional years.
- e. RTOG cosmesis scoring to be completed by physician and patient at baseline (prior to treatment), at first FU 4-6 weeks after surgery, six months and one year after surgery and then annually for 2 additional years.

9. CRITERIA FOR EVALUATION AND ENDPOINT DEFINITIONS

9.1 PATHOLOGIC RESPONSE – Standard pathologic assessment per our institutional guidelines will be followed. Additionally, we will include calculation of percent cellularity on the biopsy specimen, residual cancer burden (RCB) analysis and repeat evaluation of Ki67 and receptor status (ER, PR and Her2) if there is any residual invasive cancer at surgery. Residual cancer burden will be assessed by staff pathologists and is calculated using a published continuous index that combines pathologic measurements of the primary tumor (size and cellularity) and nodal metastases (number and size) (reference Symanns). This RCB index has been validated as a predictor of distant relapse.

9.2 ACUTE TOXICITY- Acute toxicity will be graded with the Common Terminology Criteria for Adverse Events (CTCAE) version 4. Grade ≥ 3 acute toxicity will be considered severe (Appendix 15.2).

9.3 COSMESIS- As noted in the introduction, early cosmetic results from other published pre-operative radiation series for early stage breast cancer have been favorable.¹¹ We expect similar favorable outcomes, and for the pre-operative single fraction cosmetic results to be equivalent to that of partial breast radiation results. We expect cosmesis to stabilize at 3 years following treatment and thus our endpoint will be to measure results at this timepoint. We will also assess cosmesis at specified time points per the study calendar to quantify changes in breast cosmesis over time.

Cosmetic results will be evaluated by both the patient and the physician. Patients will rate cosmesis using the Breast Cancer Treatment Outcome Scale (BCTOS), which will also be used to evaluate patient reported quality of life (Appendix 15.1). This self-report instrument has been used in a number of studies for this purpose and has both reliability and validity (reference Stanton AL, Krishnan L, Collins CA. Form or function? Part 1. Subjective cosmetic and functional correlates of quality of life in women treated with breast-conserving surgical procedures and radiotherapy. *Cancer* 91:2273-2281, 2001)

October 10, 2023

Principal Investigator: [name]

IRB IRB00128074

Patients will first complete this after informed consent, and then at multiple intervening assessment points up to 3-years of follow-up (see Study Calendar). At the same time points, patients will also score cosmesis using the RTOG 4-point scale.

The cosmetic evaluation will also be completed by the radiation oncologist or surgeon after consent and prior to treatment. This will be done using the RTOG scale, using criteria established in previous RTOG trials (Appendix 15.3).

Lastly, digital images of patients' breasts will be taken after consent and prior to initiation of treatment, as well as at later time points (see Study Calendar). Two pictures will be taken at each time point, taking care to exclude the patient's face. As done in NSABP B39, the first image will be of the breast to be treated and at a 45 degree oblique angle with arms elevated overhead. The second image should be at a straight angle and frontal view of both breasts taken in either a standing or seated position with the patient's hands on her hips, taking care to exclude her face. These pictures will be taken at baseline (prior to any treatment), at 1-year and 3-year assessment points.

10. ADVERSE EVENT REPORTING

10.1 GENERAL

Adverse event collection and reporting is a routine part of every clinical trial. This study will use the descriptions and grading scales found in the NCI Common Terminology Criteria for Adverse Events version 4.0 (CTCAE v 4.0) that is available at <http://ctep.cancer.gov/reporting//ctc.html>.

Information on all adverse events, whether reported by the participant, directly observed, or detected by physical examination, laboratory test or other means, will be collected, recorded, followed and reported as described in the following sections.

Adverse events experienced by participants will be collected and recorded from initiation of study medication, throughout the study, and within 90 days of the definitive surgery. Participants who experience an ongoing adverse event related to a study procedure and/or study medication beyond 90 days post-op will continue to be contacted by a member of the study team until the event is resolved, stabilized, or determined to be irreversible by the participating investigator.

Participants should be instructed to report any serious post-study event(s) that might reasonably be related to participation in this study. The investigator should notify the IRB and any other applicable regulatory agency of any unanticipated death or adverse event occurring after a participant has discontinued

10.2 DEFINITION OF ADVERSE EVENT (AE) Serious adverse event (SAE)

October 10, 2023

Principal Investigator: [name]

IRB IRB00128074

A serious adverse event is an undesirable sign, symptom, or medical condition which:

- is fatal or life-threatening;
- requires or prolongs inpatient hospitalization;
- results in persistent or significant disability/incapacity;
- constitutes a congenital anomaly or birth defect; or
- jeopardizes the participant and requires medical or surgical intervention to prevent one of the outcomes listed above.

Events **not** considered to be serious adverse events are hospitalizations for:

- routine treatment or monitoring of the studied indication, not associated with any deterioration in condition, or for elective procedures
- elective or pre-planned treatment for a pre-existing condition that did not worsen
- emergency outpatient treatment for an event not fulfilling the serious criteria outlined above and not resulting in inpatient admission
- respite care

